7.1.2 Celecoxib

Long term use of celecoxib may cause dyspepsia, headaches (including migraines) and borderline elevated liver function tests (which could indicate liver damage). Recently, information from three long-term studies of celecoxib has become available. In the first study, a cancer prevention study, an increased risk of heart attacks, strokes, and/or deaths resulting from heart or blood vessel disease was reported among people taking celecoxib. Approximately 1 in 100 patients enrolled in this study receiving the placebo treatment had one of these serious events. In contrast, between 2 and 3 in 100 patients taking celecoxib (between 400 and 800 mg daily) had one of these serious events. Another clinical cancer prevention study found no increased risks in patients taking celecoxib 400 mg daily. The third study, an Alzheimer's disease prevention study, did not find increased risks with celecoxib. Dosing has been suspended in all three of these studies based on the findings of the first cancer prevention study. As a result, the FDA is now evaluating the possibility that celecoxib increases the risk of heart attack, stroke, and or death resulting from heart or blood vessel disease. Known infrequent side effects of celecoxib include nausea and/or vomiting, diarrhea, flatulence, abdominal and stomach pain, bleeding ulcer, upper respiratory tract infection, pharyngitis, rhinitis, sinusitis, peripheral edema, back pain, dizziness, insomnia, and skin rash. Rare risks include sudden death (unexpected or instant death that occurs within minutes or hours from any cause other than violence), vasculitis, hepatitis, liver failure, kidney failure, blood dyscrasia, hypoglycemia, hyponatremia, viral meningitis, severe allergic reaction, visual changes, and transient ischemic attack.

Warnings/Precautions: Stomach problems may be more likely to occur if patients drink alcoholic beverages while taking this medicine. Taking two or more of the nonsteroidal anti-inflammatory drugs together on a regular basis may increase the chance of unwanted effects. Also, taking acetaminophen, aspirin or other salicylates, or ketorolac (e.g., Toradol) regularly while taking a nonsteroidal anti-inflammatory drug may increase the chance of unwanted effects. The risk will depend on how much of each medicine is taken every day and how long the medicines are taken together. Therefore, patients should not take acetaminophen or aspirin or other salicylates or ketorolac (e.g., Toradol). Clinical studies with celecoxib have identified potentially significant interactions with fluconazole and lithium. Experience with nonsteroidal anti-inflammatory drugs (NSAIDs) suggests the potential for interactions with furosemide and ACE inhibitors. Celecoxib is contraindicated in patients with known hypersensitivity to celecoxib. Celecoxib should not be given to patients who have demonstrated allergic-type reactions to sulfonamides. Celecoxib should not be given to patients who have experienced asthma, urticaria, or allergic-type reactions after taking aspirin or other NSAIDs. Severe, rarely fatal, anaphylactic-like reactions to NSAIDs have been reported in such patients.

For more risk information reference the Investigator's Brochure or package insert.

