3.2 Post-surgery Screening

3.2.1 Inclusion Criteria

1. Must have had HIPEC during surgery
2. Must have a CC score of 0
3. ECOG performance status of 0, 1 or 2
4. Able to swallow pills
5. Platelet \geq 75,000/ μ L
6. Hemoglobin \geq 9.0 g/dL
7. Hematocrit \geq 27.0%
8. WBC $>$ 2000/mm³
9. Creatinine $<$ 1.5 x institutional upper limit of normal (ULN), OR Creatinine clearance \geq 50

mL/min/1.73 m² for patients with creatinine levels greater than 1.5 x ULN

- 10. Total bilirubin \leq 1.5 x ULN
- 11. AST(SGOT) and ALT(SGPT) \leq 2.5 X ULN
- 12. Must be eligible for pheresis within 8 weeks of surgery
- 13. Availability of sufficient number of tumor cells for cryopreservation and subsequent vaccine production

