3.2.2 Exclusion Criteria

- 1. Infection of tumor tissue with pathogens resistant to radiation and fungizone
- 2. Patients on systemic immunosuppressive agents, including steroids. Patients who are able to be removed from immunosuppressives at least 5 days prior to the first vaccine will be considered eligible
- 3. Patients with active autoimmune disease or history of transplantation. Patients with indolent or chronic autoimmune disease not requiring steroid treatment are considered eligible.
- 4. Patients who are pregnant or nursing
- 5. Patients experiencing a cardiac events (acute coronary syndrome, myocardial infarction, or ischemia) within the 3 months prior to accrual
- 6. Patients with a New York Heart Association classification of III or IV
- 7. Prior allergic reaction or hypersensitivity to celecoxib or NSAIDs

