Study treatment will consist of one priming dose of DC vaccination followed by 3 booster cycles of DC vaccine + chemokine modulation regimen (CKM), cycles 1-3. The booster vaccine is administered on Monday followed by 4 days of the CKM regimen (Tuesday – Friday).

Timing of the experimental treatment:

- Priming cycle: 6 to 16 weeks after surgery (target: 8 weeks)
- Booster cycle 1: 4 to 12 weeks after priming cycle (target: 4 weeks)
- Booster cycle 2: 4 to 12 weeks after booster cycle 1 (target: 4 weeks)
- Booster cycle 3: 4 to 12 weeks after booster cycle 2 (target: 4 weeks)

It is expected that a significant proportion of the patients will undergo adjuvant clinically indicated chemotherapy. Adjuvant chemotherapy can be administered between the courses of immunotherapy, but no sooner than 5 days after finishing any cycle of immunotherapy. The following cycle of immunotherapy will start no sooner than 5 days after the last day of a chemotherapy cycle and after recovery from acute side effect of chemotherapy.

Patients who (for clinical or logistic reasons) will not be able to take any cycle of immunotherapy within the above-indicated windows, can still receive the remaining courses of immunotherapy at later time points, but will not be included in the analysis of the primary efficacy endpoint, although they can be analyzed in an exploratory manner.

Similarly, patients who (for clinical or logistic reasons) will not be able to receive the priming dose of vaccine within 3 months after surgery, can still receive immunotherapy at later time points, but will not be included in the analysis of the primary efficacy endpoint, although they can be analyzed in an exploratory manner.

In the efficacy phase, patients will receive a priming dose of the α DC1 vaccine followed by 3 courses of the α DC1 booster vaccine combined with CKM regimen as illustrated in the following table:

Eligibility	Informed Consent CRS + HIPEC
Screening	History and physical exam, ECOG performance status, blood work, evaluation of tumor material
Post-surgery (within the first 8 weeks following surgery)	Leukapheresis
Week 1* (upon recovery from surgery; no sooner than 6 weeks post-surgery)	Priming Vaccine dose; no chemokine modulation) One day: α DC1 vaccine Oral celecoxib, 200 mg, before and after treatment on the day of vaccination
Weeks 2-3	Rest
Week 4 (target)*	Booster Cycle 1 Monday: α DC1 vaccine

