	Tues – Fri: Systemic Chemokine Modulation Regimen. Oral celecoxib, 200 mg, twice daily on the days of vaccination and CKM. Celecoxib will be discontinued after CKM on Friday. Rintatolimod is only administered on Wednesday and Friday.
Week 5-7	Rest
Week 8 (target)**	Booster Cycle 2 Monday: α DC1 vaccine. Reintroduce oral celecoxib, 200 mg, twice daily on the days of vaccination and CKM. Tues – Fri: Systemic Chemokine Modulation Regimen. Rintatolimod is only administered on Wednesday and Friday. Celecoxib will be discontinued after CKM on Friday.
Week 9-11	Rest
Week 12 (target)**	Booster Cycle 3 Monday: α DC1 vaccine. Tues – Fri: Systemic Chemokine Modulation Regimen. Rintatolimod is only administered on Wednesday and Friday. Oral celecoxib, 200 mg, twice daily, will be given on the days of vaccination and CKM. Celecoxib will be discontinued after CKM on Friday.
Off study treatment	Follow-up for Time-to-Progression/occurrence (TTP)

CRS: Cytoreductive surgery; HIPEC: Hyperthermic intraperitoneal chemoperfusion; TTP: Time-to-progression

*Adjuvant immunotherapy may be delayed until recovery at the discretion of the investigator/sub-investigator. The beginning of immunotherapy will be considered week 1 of the experimental treatment and the timing of all subsequent elements of treatment will be based upon the first vaccine.

**Patients may receive postoperative (standard of care, adjuvant) chemotherapy at the discretion of the treating oncologist. Adjuvant chemotherapy may start 5 days after the first full cycle of immunotherapy (first booster vaccine + CKM). Following completion of adjuvant chemotherapy, subsequent immunotherapy can start after 5 days post adjuvant chemotherapy.

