5.4 Agent Administration

5.4.1 Celecoxib

The drug will be administered orally, at a dose of 200 mg, twice daily on all study treatment days only.

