8.2 Celecoxib

A sulfa non-steroidal anti-inflammatory drug (NSAID) used in the treatment of osteoarthritis, rheumatoid arthritis, acute pain, painful menstruation and menstrual symptoms, and to reduce numbers of colon and rectum polyps in patients with familial adenomatous polyposis.

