8.2.3 Preparing and dispensing

Externally prepared and dispensed per treating physician prescription. Drug storage and accountability

Store at room temperature at 77 °F (25 °C) away from light and moisture. Brief storage between 59-86 °F (15-30 °C) is permitted.

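### Exclusion 7 omits prior sulfonamide reactions, although Section 7.1.2 bars celecoxib after them and celecoxib is scheduled on every treatment day

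*Combined protocol and SAP*

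**What the plan says.** Under Warnings/Precautions, Section 7.1.2 identifies three histories that rule out celecoxib: hypersensitivity to the drug itself, reactions to sulfonamides, and reactions to aspirin or other NSAIDs. The second is stated as "Celecoxib should not be given to patients who have demonstrated allergic-type reactions to sulfonamides". Section 8.2 describes the drug in the same terms: "A sulfa non-steroidal anti-inflammatory drug (NSAID) used in the treatment of osteoarthritis".

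The only drug-allergy criterion is item 7 of Section 3.2.2: "Prior allergic reaction or hypersensitivity to celecoxib or NSAIDs".

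Celecoxib is part of the regimen throughout. Section 5.4.1 states: "The drug will be administered orally, at a dose of 200 mg, twice daily on all study treatment days only". In the Phase 2 table of Section 5.2, the priming entry is "Oral celecoxib, 200 mg, before and after treatment on the day of vaccination" and the entry for booster cycle 1 is "Oral celecoxib, 200 mg, twice daily on the days of vaccination and CKM", with equivalent entries for cycles 2 and 3. Section 5.1 fixes the celecoxib dose in Phase 1, and Section 6.2.2 exempts it from dose reduction in Phase 2. Item 4 of Section 3.2.1 also requires patients to be "Able to swallow pills". On supply, Section 8.2.3 says "Externally prepared and dispensed per treating physician prescription".

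**The concern.** The protocol states a restriction on giving one of its own study drugs, but the entry criteria do not screen for it. A patient with a known sulfonamide reaction can pass every numbered criterion and then be scheduled for celecoxib. If staff notice and withhold it, the protocol does not say what follows. The patient might be ineligible, or might be treated without one of the three CKM drugs. If treated, it is unclear whether the patient counts in the primary efficacy analysis. The plan answers that last question for other departures: missed cycle windows and late priming (Section 5.2) and a low vaccine cell number (Section 8.1.2) remove a patient from the primary analysis. It says nothing about omitted celecoxib.

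If staff do not notice, the stake is an avoidable allergic reaction. There is also a possible knock-on effect. On the priming day the patient receives vaccine and celecoxib but neither interferon nor rintatolimod. A grade 2 allergic reaction judged even possibly related to the vaccine is a regimen-limiting toxicity under Section 5.1, and one attributed to the vaccine ends study treatment under Section 6.2.1. A celecoxib reaction could therefore be counted against the vaccine.

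**Working it through.** The plan gives no figure to reproduce here. The check compares the warning with the eligibility text and then counts scheduled exposure.

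**Step 1: allergy groups in Section 7.1.2 against item 7 of Section 3.2.2**

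| Prior reaction named in 7.1.2 | In item 7? |
|---|---|
| Celecoxib | Yes |
| Sulfonamides | No |
| Aspirin or other NSAIDs | Yes, as NSAIDs |

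Groups named: 3. Carried over: 2. Missing: 3 − 2 = 1.

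**Step 2: can item 7 be read to include sulfonamides?** No. Section 7.1.2 lists them separately from NSAIDs. The word celecoxib does not cover them either, because a sulfonamide-allergic patient who has never taken celecoxib has no celecoxib reaction to report.

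**Step 3: is the group caught elsewhere?** Sections 3.1, 3.2.1 and 3.2.2 do not mention it. Section 3.5 adds an exclusion for immune deficiency outside the numbered lists, but nothing on sulfonamides.

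**Step 4: is celecoxib avoidable within the regimen?** No celecoxib-free option is defined for such a patient. Section 6.2.2 lets a patient stop CKM and continue the vaccine, but only after toxicity. The hypersensitivity rules in Section 6.4 cover interferon and the TLR3 ligand and do not name celecoxib.

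**Step 5: scheduled exposure in a full Phase 2 course (Sections 5.2 and 5.4.1)**

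- Days = 1 priming day + 3 booster cycles × 5 days (Monday to Friday) = 1 + 15 = 16.
- Doses = 16 days × 2 per day = 32.
- Amount = 32 × 200 mg = 6,400 mg.

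This count follows the Phase 2 treatment text. The Phase 1 timeline in Section 5.1 adds once-daily dosing between the two vaccines, and Section 2.6.2 describes daily dosing from surgical discharge, so exposure under those texts is longer. The count shows that celecoxib is integral to the regimen. It does not measure how many patients are at risk or how much harm would follow.

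**The case against.** The strongest reply is that Section 7.1.2 is itself protocol text. Meeting the entry criteria does not authorise giving a drug that another section says to withhold: one section governs entry, the other administration, and the two do not contradict each other. A treating physician prescribes celecoxib, history and physical examination are scheduled at screening and at every cycle (Section 10), and 7.1.2 refers the reader to the package insert. The protocol also foresees patients who receive less than the full combination (Section 6.2.2) and lets the investigator stop treatment when a patient's condition makes it unacceptable (Section 5.7). The exemption from dose reduction concerns toxicity and does not override a warning.

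Much of this stands. These are real safeguards, and they make an unguarded exposure less likely. The pill-swallowing criterion adds little: the protocol does not tie it to celecoxib, and some CKM pre-medications have no stated route. There is also no basis for calling the affected group either small or large.

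The reply does not settle eligibility. Withholding celecoxib leaves open whether the patient may enter and, if so, on what regimen and in which analysis. The provisions in Sections 5.7 and 6.2.2 are not written for a contraindication known before the first dose.

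**Conclusion.** The concern holds as a minor point. One of the three prior-allergy groups in Section 7.1.2 is missing from the entry criteria, and celecoxib is scheduled on all 16 treatment days of a full Phase 2 course. Confidence in the omission is high, because it rests only on the protocol's own wording and needs no view on cross-reactivity. Any effect on patients cannot be sized: the documents give neither the frequency of sulfonamide allergy nor a reaction rate. The misattribution route through the vaccine toxicity rules is possible but equally unquantified. The planned 168 patients, 90% power and alpha of 0.10 do not change.

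**What to change.** Add sulfonamides to item 7 of Section 3.2.2, so that it names celecoxib, sulfonamides, and aspirin or other NSAIDs. Aspirin is arguably already covered as an NSAID; naming it only makes the item match Section 7.1.2. This aligns entry with the existing warning and settles that such patients are ineligible. It costs one line of text and makes an unknown number of patients ineligible.

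If the sponsor would rather keep these patients, the alternative is to define a regimen without celecoxib and state whether those treated with it enter the primary efficacy analysis. That takes more drafting and puts a second regimen into a single-arm comparison, so the exclusion is the simpler choice.

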7.1.3 Interferon- α 2b

IFN α may cause fever, chills and flu-like symptoms; loss of appetite; nausea; vomiting, diarrhea and abdominal pain; fatigue; lowered white blood count may increase risk of infection; lowered

platelets may lead to an increase in bruising or bleeding; hair loss. Other risks which may be common in cases of prolonged administration include drowsiness; temporary confusion; anxiety, amnesia, irritability, confusion, delusions and depression which can be severe; numbness and/or tingling in the hands and/or feet, skin rashes and inflammation of the pancreas. Inflammation of the pancreas is swelling or irritation of the pancreas which may result in tenderness or pain in the stomach and/or back. When the pancreas is inflamed, the body is not able to absorb all the nutrients it needs.

For more risk information reference the Investigator's Brochure or package insert.

7.1.4 Rintatolimod (poly IC analog)

Clinical experience with rintatolimod totals over 800 patients with more than 400 patients receiving Ampligen® for at least six (6) months, greater than 200 patients for one (1) year, over 50 patients up to two (2) years, and with 20 or more patients over two (2) years at doses as high as 1200 mg i.v. twice weekly. No evidence of dose-limiting organ toxicity, including hematologic, liver, or renal toxicity, has been observed.

Adverse events related to infusion such as mild flu-like symptoms, transient headache, fever, myalgia, arthralgia, and fatigue/malaise which were seen, usually occur during the initial weeks of treatment and tend to subside on repeated administration. These side events were seen in Chronic Fatigue Syndrome patients, cancer patients, chronic hepatitis B infected patients and individuals infected with HIV at doses of 200 and 400 mg and higher. Patients that experience these minor side effects can continue on Ampligen® and as noted, these signs and symptoms typically subside after several weeks of continued treatment. Specific symptoms of note include a flushing reaction, characterized by at least one occurrence of erythema of the face, neck and chest, which has been observed in approximately 10% of patients treated in various studies. Usually the flushing is both mild and transient and disappears with repeated dosing.

Occasionally, it can be accompanied by a tightness of the chest, tachycardia, anxiety, shortness of breath, subjective reports of "feeling hot", diaphoresis and nausea. The reaction is usually infusion-rate dependent and may generally be controlled by slowing the infusion rate. An antihistamine (diphenhydramine hydrochloride) can be helpful in controlling and reducing the response in the occasional patient for whom the symptom persists. Other less frequently occurring adverse effects include nausea, diarrhea, itching, urticaria, bronchospasm, transient hypotension, photophobia, rash, bradycardia and transient visual disturbances. A severe unexpected local reaction to extravasation of rintatolimod (Ampligen®, Poly I:Poly C₁₂U) at the infusion site in the dorsum of the left hand was reported in a Chronic Fatigue Syndrome patient with chilblains. Several patients experienced liver enzyme level elevations while receiving Ampligen® associated with chronic dosing over many weeks.

Rintatolimod has been dosed in combination with alpha interferon in investigator initiated studies under investigator IND applications during the period between December 1985 and April 1994. A total of 24 patients received combination treatments. Clinical conditions included renal cell carcinoma, chronic myelogenous leukemia, melanoma, and ovarian cancer. Rintatolimod was given as an IV infusion at a dose of 300 mg BIW. The starting dose was sometimes as low as 1-10 mg. The interferons were administered at a dose of 3 million Units daily, with some doses of 0.75 mU at the low side and up to 6 mU at the higher side.

The therapy with rintatolimod in combination with alpha interferon was generally well tolerated without evidence of dose-limiting or cumulative toxicities. The most frequent adverse reactions were considered minor in severity and duration. Most of them were flu-like symptoms such as chills, cold feeling, fatigue, decreased appetite, fever, muscular aches. Also shortness of breath has been seen as well as hypotension, nausea, anemia, dyspnea, numbness, itching and blurred vision. These adverse events were judged possibly related to the condition of the patients, but also possibly related to the administration of rintatolimod or interferon. In some cases worsening of the patient's condition has been seen due to tumor progression, but in general favorable clinical patterns were observed in these patients with advanced disease. Such combinations were not intended to be immune modulating and were evaluated in the context of clinical cancer care.

For more risk information reference the Investigator's Brochure.

7.2 Definitions

Adverse event (AE) means any untoward medical occurrence associated with the use of a drug in humans, whether or not considered drug related.

Adverse reaction means any adverse event caused by a drug.

Suspected adverse reaction means any adverse event for which there is a reasonable possibility that the drug caused the adverse event. Suspected adverse reaction implies a lesser degree of certainty about causality than "adverse reaction".

Reasonable possibility, for the purpose of IND safety reporting, means there is evidence to suggest a causal relationship between the drug and the adverse event.

Life-threatening, suspected adverse reaction is considered "life-threatening" if, in the view of either the investigator (i.e., study site principal investigator) or sponsor, its occurrence places the patient or subject at immediate risk of death. It does not include a suspected adverse reaction that, had it occurred in a more severe form, might have caused death.

Serious, suspected adverse reaction is considered "serious" if, in the view of either the investigator (i.e., study site principal investigator) or sponsor, it results in any of the following outcomes: death, a life-threatening adverse reaction, inpatient hospitalization or prolongation of existing hospitalization, a persistent or significant incapacity or substantial disruption of the ability to conduct normal life functions, or a congenital anomaly/birth defect.

Important medical events that may not result in death, be life-threatening, or require hospitalization may be considered serious when, based upon appropriate medical judgment, they may jeopardize the patient or subject and may require medical or surgical intervention to prevent one of the outcomes listed in this definition. Examples of such medical events include allergic bronchospasm requiring intensive treatment in the emergency room or at home, blood dyscrasias or convulsions that do not result in inpatient hospitalization, or the development of drug dependency or drug abuse.

Unexpected, suspected adverse reaction is considered "unexpected" if it is not listed in the general investigational plan, clinical protocol, or elsewhere in the current IND application; or is not listed at the specificity or severity that has been previously observed and/or specified.

